1.2.1.2.3. Progression Free Survival and 6 month PFS rate per RECIST (v1.1)

Progression-Free Survival (PFS) per RECIST (v1.1) is defined as the time from the date of the first dose of study treatment to the first objective documentation of disease progression by RECIST (v.1.1) or death by any cause, whichever comes first. If a patient has not progressed or died at the time of analysis (up to the date of data cutoff), PFS will be censored on the date of the last tumor assessment (up to the date of data cutoff).

PFS in months is calculated as (first event date/censored date – date of first dose +1)/30.4375.

Table 2 summarizes the censoring rules for the PFS analysis.

Table 2: PFS Definition: Events and Censoring Reasons and Hierarchy

Hierarchy Censoring	Situation	Date of Event or Censor	Event / Censor
1	No baseline radiological tumor assessment available	Date of first dose	Censor
5	No post baseline radiological tumor assessment available and no death reported within 2 scan intervals following the first dose date.	Date of first dose	Censor
	No post baseline radiological tumor assessment available but death reported within 2 scan intervals following the first dose date	Date of death	Event
6	No tumor progression (per RECIST 1.1) and no death reported within 2 scan intervals following last adequate radiological tumor assessment	Date of last adequate radiological tumor assessment	Censor
	No tumor progression (per RECIST 1.1) but death reported within 2 scan intervals following last adequate radiological tumor assessment	Date of death	Event
	Tumor progression (per RECIST 1.1) documented within 2 scan intervals following previous adequate radiological tumor assessment	Earliest of the target, non-target and new tumor assessment dates	Event
3	Tumor progression (per RECIST 1.1) documented after 2 scan intervals following previous adequate radiological tumor assessment	Date of previous adequate radiological assessment	Censor
2	New anticancer treatment started and no tumor progression	Date of previous adequate radiological assessment immediately prior to start of new therapy	Censor
4	No tumor progression (per RECIST 1.1) and patient lost to follow-up or withdrawal of consent	Date of last adequate radiological Assessment	Censor

Notes: (1) Symptomatic deteriorations (i.e. symptomatic progressions, which are not radiographically confirmed) will not be considered as progressions.

(2) If target, non-target, and new lesion assessments have different dates within a visit, then the earliest of those dates will be considered as the date of the tumor assessment if the assessment for that visit is progressive disease (PD); otherwise the latest date will be used.

(3) Adequate radiographical tumor assessment refers to an assessment with overall response of CR, PR, SD, non-CR/non-PD, or PD.

Two scan intervals are 88 days (12 weeks+ 4 days) if previous assessment is within 124 days (18 weeks – 2 days) from the first dose date; or 130 days (18 weeks + 4 days) if previous assessment is after 124 days but prior to 146 (24 weeks – 2 day) days from the first dose date, or 172 days (24 weeks + 4 days) if previous assessment is after 146 days from the first dose date.

The 6-month PFS Rate per RECIST (v1.1) is defined as the proportion of patients who neither progressed by RECIST (v.1.1) nor died before 6 months from the first study treatment.

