Adverse events p		X	X	X	X	X	X	X	X	X	X	X	
Administer DSP-7888 Dosing Emulsion			X	X	X	X	X	X	X	X	X		
Administer nivolumab							X	X	X	X	X		
Follow-up for overall survival													X q
Objective disease assessment f		X	First post-treatment assessment at Week 4 (Cycle 3), followed by one at Week 12 (Cycle 7), then 2 subsequent assessments every 6 weeks at Week 18, Week 24 (Cycle 10, Cycle 13), and finally every 12 weeks (Cycle 19 and every 6 cycles) until disease progression. s										

Abbreviations: AE = adverse event; CT = computed tomography; CTCAE = Common Terminology Criteria for Adverse Events; CTL = cytotoxic T lymphocyte; ECG = echocardiogram; ECOG = Eastern Cooperative Oncology Group; ECHO = echocardiogram; FFPE = formalin-fixed and paraffin embedded; HIV = human immunodeficiency virus; HLA = human leukocyte antigen; ICF = informed consent form; iRECIST = immune Response Evaluation Criteria in Solid Tumors MRI = magnetic resonance imaging; MUGA = multiple gated acquisition; OS = overall survival; PD-L1 = programmed death ligand 1; PET = positron emission tomography; PBMC = peripheral blood mononuclear cells; RECIST = Response Evaluation Criteria in Solid Tumors; TIL = tumor-infiltrating lymphocytes; TIS = tumor immune signature; WT1 = Wilms Tumor 1

a All tests must be performed PRIOR to injection of study treatment, with the exception of ECG.

b Complete End of Treatment assessment procedures before patient receives new anti-cancer treatment.

c Inspection of prior injection sites will be done at each administration of the vaccine.

d . From Cycle 4, ECHO/MUGA tests for ejection fraction will be done on Day 1 every 6th cycle (eg, Cycle 10, 16, 22).

e Obtained at least 2 hours post-dose of DSP-7888 Dosing Emulsion.

f From Cycle 4, 12-lead electrocardiograms will be performed on Day 1 of every 3rd Cycle (eg, Cycle 7, 10, 13).

g It should be ensured that a total of at least 23 slides of archival samples and/or the equivalent amount of archival tissue block and/or fresh biopsy samples from the enrolled patients are available. These samples must contain sufficient tumor tissue.

- h Collection of tumor tissue samples at Pre-Study evaluation is mandatory. Either archival tissue or fresh biopsy samples at Pre-study evaluation would be acceptable. Collection of fresh biopsy samples is required, if medically feasible.

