**Table 9: Schedule of Assessments (Phase 2, Combination of DSP-7888 Dosing Emulsion and Pembrolizumab for Ovarian Cancer)**

Period	Pre-screening	Screening period	Treatment Period (All procedure must be performed PRIOR to injection of study treatment)										Follow-up Period		Notes
			1			2			3	4	5+*	EOT (30 day after last dose)	Disease follow up**	Survival Follow up	
			1	8	15	1	8	15	1	1	1				
			0	1	2	3	4	5	6	9	12				
Scheduling Window (Days)	-	-28 to 1*	0	±2	±2	±2	±2	±2	±3	±3	±7	+7 a	±7	±14	*Procedures in screening should be completed within 28 days from Cycle 1 Day1
Study Drug Administration															
DSP-7888 Dosing Emulsion			X	X	X	X			X	X	X				
Pembrolizumab						X			X	X	X				
Administrative procedure															
HLA screening informed consent	X														
Informed Consent*		X													*Main informed consent and informed consent for future biomarker (optional) for willing participants
Inclusion and Exclusion criteria		X													
Demography and Medical History		X*													*including COVID-19 history and vaccination history
Prior and Concomitant Medications		X	X	X	X	X			X	X	X	X			
Cancer history and Cancer Prior Treatment		X													

Period	Pre-screening	Screening period	Treatment Period (All procedure must be performed PRIOR to injection of study treatment)										Follow-up Period		Notes	
			1			2			3	4	5+*	EOT (30 day after last dose)	Disease follow up**	Survival Follow up		
Treatment Cycle	Day	Week (from 1 st dose)	1	8	15	1	8	15	1	1	1					
Scheduling Window (Days)	-	-28 to 1*	0	±2	±2	±2	±2	±2	±2	±3	±3	±7	+7 a	±7	±14	
New anticancer therapy														X	X	*Every 12 weeks up to 105 weeks and/or on an ad-hoc basis for safety or regulatory purposes, or a prespecified analysis.
Safety assessment																
Physical Examination*		X	X			X				X	X	X	X			*Inspection of prior injection site will be done
Vital Sign and Weight		X*	X	X	X	X				X	X	X	X			*Height will be measured only at screening
12-lead ECG		X								X			X			
ECHO/MUGA		X														
ECOG performance status		X	X	X	X	X				X	X	X	X			
Adverse Events	X*	X**	X	X	X	X				X	X	X	X**			* SAE related to study procedure will be reported to ██████████ Safety **AE must be collected from the date of main ICF to 30 days after last dose

Period	Pre-screening	Screening period	Treatment Period (All procedure must be performed PRIOR to injection of study treatment)										Follow-up Period		Notes	

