Objective disease assessments will be performed according to RECIST (v1.1) and iRECIST, with the first assessment performed at the end of the dose-limiting toxicity (DLT) period (Cycle 3: at 4 weeks for nivolumab arm, at 6 weeks for pembrolizumab arm), and at Weeks 12, 18, and 24 after the first dose of DSP-7888 Dosing Emulsion. After that, objective disease assessments will occur every 12 weeks until disease progression.

1.2.1.2.1. Best Overall Responses, Objective Response Rate and Disease Control Rate, and Duration of Response per RECIST (v1.1)

Objective disease assessments will be performed according to RECIST (v1.1) and iRECIST, with the first assessment performed at the end of the dose-limiting toxicity (DLT) period (Cycle 3: at 4 weeks for nivolumab arm, at 6 weeks for pembrolizumab arm), and at Weeks 12, 18, and 24 after the first dose of DSP-7888 Dosing Emulsion. After that, objective disease assessments will occur every 12 weeks until disease progression.

Best Overall Response (BOR) per RECIST (v1.1) is the best response recorded from first dose until disease progression or start of new anti-cancer therapy. Tumor scan assessment done after PD or after “new anti-cancer” treatment will not be considered in the evaluation of BOR. BOR is derived from the sequence of objective response determined by the following order:

- CR: One objective status of CR documented and confirmed (at least 4 weeks after) before progression or start of new anti-cancer therapy
- PR: One objective status of PR documented and confirmed (at least 4 weeks after) before progression or start of new anti-cancer therapy, but not qualifying as CR
- SD: At least 1 objective status of SD or better documented at least 1 nominal scan interval (6 weeks – 2 days window = 40 days) after first dose date and before progression and the start of new anti-cancer therapy, but not qualifying as CR or PR
- PD: Progression documented within 2 nominal scan intervals (or 12 weeks + 2 days window = 86) after first dose date and not qualifying as CR, PR, or SD
- NE: All other cases will be categorized as NE.

Objective Response Rate (ORR) per RECIST (v1.1) is defined as the proportion of patients who have achieved confirmed complete response (CR) or partial response (PR), evaluated using RECIST (v1.1) by investigator assessment.

The patients will be considered as non-responders until proven otherwise. Thus, the patients who:

- Do not have CR or PR while on study; or

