5.5. Efficacy Analyses

As the study was terminated for phase 2 portion due to the interim monitoring for efficacy. The final CSR will focus on the safety updates for the study as a synoptic CSR. As a result, there will no analysis included for efficacy portion. The timepoint overall response evaluation, BOR, ORR, DCR and DOR based on RECIST 1.1 will be listed.

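### The SAP's day limits for PFS censoring and best response do not fit Arm 1's Week 4 to Week 12 gap or the wider Phase 2 visit windows, and one band edge is misprinted

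*SAP*

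**What the plan says.** **PFS.** SAP 1.2.1.2.3, Table 2, censors at the previous adequate scan in this situation: "Tumor progression (per RECIST 1.1) documented after 2 scan intervals following previous adequate radiological tumor assessment". The text below the table sets the length by the day of the previous scan:

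- early band: "Two scan intervals are 88 days (12 weeks+ 4 days) if previous assessment is within 124 days" from first dose;
- middle band: "130 days (18 weeks + 4 days) if previous assessment is after 124 days but prior to 146 (24 weeks – 2 day) days";
- late band: "172 days (24 weeks + 4 days) if previous assessment is after 146 days from the first dose date".

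The same lengths decide whether a death after the last adequate scan counts as an event, and SAP 1.2.1.2.4 carries them over to iPFS.

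**Best response.** SAP 1.2.1.2.1 requires SD at least 40 days after first dose and limits PD as follows: "PD: Progression documented within 2 nominal scan intervals (or 12 weeks + 2 days window = 86) after first dose date". Anything else is NE.

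**Scope.** SAP 1.2.2.1 and 1.2.2.2 apply these definitions to Phase 2 unchanged.

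**Schedules.** Protocol Table 7 says of Arm 1: "First post-treatment assessment at Week 4 (Cycle 3), followed by one at Week 12 (Cycle 7"), then Weeks 18 and 24, then every 12 weeks. Arm 2 and Phase 2 scan at Weeks 6, 12, 18 and 24, then every 12 weeks (Protocol 11.2). Visit windows are ±2 days in Phase 1b (Tables 7 and 8). In Phase 2 they are ±3 days at Cycles 3 and 4 and ±7 days from Cycle 5 (Table 9), and Table 9 ties imaging to those cycle visits.

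**Reporting.** SAP 5 and 5.5 drop efficacy analysis from the final CSR, but "The timepoint overall response evaluation, BOR, ORR, DCR and DOR based on RECIST 1.1 will be listed".

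**The concern.** A two-interval allowance is meant to tolerate one missed scan and to censor only after a longer gap. It does so only if the day count equals two scheduled gaps plus the visit windows. Where the count is too short, a progression that was actually observed is removed and follow-up ends at an earlier scan. That censoring depends on the outcome and tends to lengthen PFS. The best-response limits work the same way: if they are tighter than the protocol window, a patient scanned on an allowed date can lose an SD or PD label.

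**Working it through.** **1. Reproduce the SAP figures.** 12×7+4 = 88; 18×7−2 = 124; 18×7+4 = 130; 24×7+4 = 172; 6×7−2 = 40; 12×7+2 = 86. All agree. One does not: 24×7−2 = 166, where the SAP prints 146.

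**2. Method.** Take every in-window pair (day of previous scan, day of progression scan), counted from first dose, with scans missed in between, and apply the SAP limit. A previous scan on day 124 is read as lying within the early band. The counts below are date pairs, not probabilities.

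**3. Arm 1 (±2 days), one scan missed.**

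- Week 12 missed, Week 4 to 18: nominal gap (18−4)×7 = 98, range 94 to 102, limit 88. All 25 of 25 pairs are censored back to Week 4.
- Week 4 missed: 82 to 86 from first dose, limit 88. Tolerated.
- Week 18 missed: 80 to 88, limit 88. Tolerated.
- Week 24 missed: 122 to 130, limit 130. Tolerated unless the Week 18 scan fell on day 124, which puts it in the 88-day band (5 of 25 pairs).
- Week 36 missed: 164 to 172, limit 172. Tolerated.

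Arm 2 has only the day-124 boundary case.

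**4. Phase 2 (±3 days at Week 6, ±7 from Week 12).** With no scan missed, the largest gap is 56 days up to Week 24 (smallest limit 88) and 98 days after it (limit 172), so nothing is censored. With one scan missed:

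| Previous scan to progression | In-window gap (days) | SAP limit | Pairs censored |
|---|---|---|---|
| First dose to Week 12 | 77–91 | 88 | 3/15 |
| Week 6 to 18 | 74–94 | 88 | 21/105 |
| Week 12 to 24 | 70–98 | 88 | 55/225 (24%) |
| Week 18 to 36 | 112–140 | 88 or 130 | 100/225 (44%) |
| Week 24 to 48 | 154–182 | 172 | 55/225 (24%) |

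The 55 arises because a gap exceeds the limit when the two dates drift apart by 5 days or more: 10+9+…+1 = 55. For Weeks 18 to 36, the six dates 119 to 124 fall in the 88-day band and always fail (6×15 = 90). Dates 125 to 128 add 4+3+2+1 = 10.

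**5. Phase 2 best response.** The in-window Week 6 dates are days 39 to 45, and day 39 (1 of 7) cannot give SD. The in-window Week 12 dates are days 77 to 91, and PD on days 87 to 91 (5 of 15) fails the 86-day limit. It becomes NE when no qualifying SD or response came earlier. With both scans done, this needs SD on day 39 followed by PD on days 87 to 91: 1×5 of 7×15 = 5/105 date pairs, about 5%. If the Week 6 scan was missed, it is 5/15.

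**6. The 146/166 edge.** As printed, a previous scan on days 147 to 165 gets 172 days instead of 130, and day 146 is in no band. No in-window Phase 1b scan falls there (Week 18 is days 124 to 128, Week 24 is days 166 to 170). In Phase 2, in-window Week 24 scans on days 161 to 165 do. Simply printing 166 for Phase 2 would give those scans 130 days, and a Week 48 progression after a missed Week 36 scan (at least 154 days later) would then always be censored. Phase 2 therefore needs its own edge.

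**The case against.** The strongest reply is that the main consequence has no output. PFS, iPFS and the 6-month rate are neither analysed nor listed in the final CSR, and the definition of DOR does not use the 88, 130 and 172-day limits. That stands. The PFS part matters only if an additional analysis is run, which SAP 5 permits.

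Three stronger readings are tempting, and the documents do not support them:

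- A reader might infer that any single missed scan censors an Arm 1 progression. Only a missed Week 12 after Week 4 always does so, apart from the day-124 case.
- A reader might infer that in-window Phase 2 scans are by themselves misclassified for PFS. A scan must also have been missed.
- A reader might infer that the rules assume 6-weekly scanning throughout. The 130- and 172-day bands do allow for the change to 12-weekly scans.

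It is also fair to say that numbers may be small. The documents give no missed-scan rate, and Protocol 4.3.2 reports 7 patients in the nivolumab arm of the dose search part at 16 December 2019. PD and NE both count as no disease control, so that relabelling leaves DCR unchanged. The minimum time for SD is partly a response criterion: the best-response table in Protocol Appendix 2 and SAP Appendix 1 asks for SD more than 6 weeks from baseline, so a day-39 scan that fails to give SD is not clearly mislabelled.

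What survives is that the limits contradict the schedules they are applied to, and that the best-response limits still feed a listing.

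**Conclusion.** The limits are wrong for two of the settings they govern. In Arm 1 the failure is certain but confined to a missed Week 12 scan after Week 4. In Phase 2, 20% (3/15 and 21/105) to 44% of in-window date pairs are censored after one missed scan, and none otherwise. The live effect is on the best-response listing: an in-window Phase 2 PD on days 87 to 91 turns into NE when nothing qualifying preceded it. DCR changes only for a day-39 SD with no later SD or better. ORR, the Phase 2 primary endpoint, does not use these limits.

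This rests on windows centred on nominal days from first dose, and on the gap before the first post-baseline scan being measured from first dose. The SAP does not say whether the baseline scan is used instead. If it were, up to 28 days before first dose, a Week 12 progression after a missed first scan could be 84+28 = 112 days away, before any window, and exceed 88 in any cohort. Reading the pair counts as probabilities would also require dates spread evenly within the windows. How many patients are affected cannot be told from the documents.

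**What to change.** - **Principle.** In SAP 1.2.1.2.3 and 1.2.1.2.4, censor only when two consecutive scheduled scans were missed, using each part's own schedule and window. State whether the first gap runs from first dose or from the baseline scan.
- **Phase 1b.** Add an Arm 1 branch for a previous scan at Week 4: 98 days plus window, that is 98+4 = 102. Correct 146 to 166. Put days 124 and 166 themselves in the later bands.
- **Phase 2.** Use 84+7 = 91 days (first dose to Week 12), 84+3+7 = 94 (Week 6 to 18), 84+14 = 98 (Week 12 to 24), 126+14 = 140 (Week 18 to 36) and 168+14 = 182 (Week 24 to 48 and later). Set the band edges at 126−7 = 119 and 168−7 = 161, each belonging to the later band. These limits still censor after two missed scans, where the shortest in-window gaps are 119, 116, 154, 196 and 238 days respectively.
- **Best response, Phase 2.** Set the PD limit at 84+7 = 91 days. Reconcile the minimum SD time (40 days, or 39 with the Phase 2 window) with the appendix requirement of more than 6 weeks from baseline, and state one rule. The 40-day rule for iSD in SAP 1.2.1.2.2 should follow it.

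The cost is SAP wording and programming only. No data collection or visit changes.

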1.2.1.2.4. Progression Free Survival and 6 month PFS rate per iRECIST

Immune Progression-Free Survival (iPFS) is defined as the time from the date of the first dose of study treatment to the first objective documentation of disease progression by iRECIST or death by any cause, whichever comes first. If a patient has not progressed or died at the time of analysis (up to the date of data cutoff), iPFS will be censored on the date of the last tumor assessment (up to the date of data cutoff).

The event date to be used for calculation of iPFS should be the first date at which progression criteria are met (ie, the date of immune unconfirmed progressive disease [iUPD]) provided that immune confirmed progressive disease [iCPD] is confirmed at the next assessment. If iUPD occurs, but is disregarded because of later iSD, iPR, or iCR, that iUPD date should not be used as the progression event date. Patients with iUPD at their last assessment were assigned a date of progression at the earliest timepoint iUPD was consecutively determined for that patient (ie, sequential iUPD determinations without an intervening iSD, iPR, or iCR determination).

iPFS in months is calculated as (first event date/censored date – date of first dose +1)/30.4375.

As patients who remain on study treatment following objective disease progression per RECIST (v.1.1) will continue to be evaluated for objective response to study treatment according to the SOA and to iRECIST, the censoring rules for iPFS is defined different from PFS.

Table 3 summarizes the censoring rules for the iPFS analysis.

Table 3: iPFS Definition: Events and Censoring Reasons and Hierarchy

Hierarchy Censoring	Situation	Date of Event or Censor	Event / Censor
1	No baseline radiological tumor assessment available	Date of first dose	Censor
5	No post baseline radiological tumor assessment available and no death reported within 2 scan intervals following the first dose date	Date of first dose	Censor
	No post baseline radiological tumor assessment available but death reported within 2 scan intervals following the first dose date	Date of death	Event
6	No tumor progression (iUPD/iCPD) per iRECIST and no death reported within 2 scan intervals following last adequate radiological tumor assessment	Date of last adequate radiological tumor assessment	Censor
	No tumor progression (iUPD/iCPD) per iRECIST but death reported within 2 scan intervals following last adequate radiological tumor assessment	Date of death	Event
	Tumor progression (iCPD per iRECIST) documented.	Date of iCPD	Event
	Tumor progression (iUPD at their last assessment but sequential iUPD determinations without an intervening iSD, iPR, or iCR determination)	Date of the earliest iUPD date.	Event

Hierarchy Censoring	Situation	Date of Event or Censor	Event / Censor
3	Tumor progression (iUPD per iRECIST) but didn't confirmed later or intervening of iSD, iPR or iCR	Date of last adequate radiological assessment.	Censor
2	New anticancer treatment started and no tumor progression (iCPD or iUPD)	Date of previous adequate radiological assessment immediately prior to start of new therapy	Censor
4	No tumor progression (iUPD/iCPD) and patient lost to follow-up or withdrawal of consent	Date of last adequate radiological Assessment	Censor

Notes:

(1) If target, non-target, and new lesion assessments have different dates within a visit, then the earliest of those dates will be considered as the date of the tumor assessment if the assessment for that visit is progressive disease (iUPD or iCPD); otherwise the latest date will be used.

(2) Adequate radiographical tumor assessment refers to an assessment with overall response of iCR, iPR, iSD, iUPD, iCPD.

Two scan intervals are same as defined for PFS derivation.

The 6-month iPFS Rate per iRECIST is defined as the proportion of patients who neither progressed by iRECIST nor died before 6 months from the first study treatment.

